5.0 SELECTION OF STUDY POPULATION

Inclusion Criteria:

- Male or Female age 40-80
- A Clinical diagnosis of COPD as defined by GOLD
- At Least a 10 pack year smoking history
- Exhibit symptoms of chronic bronchitis as defined by the Medical Research Council
- FEV1% predicted \geq 35% and \leq 70% Post Bronchodilator
- Clinically stable in the last 4 weeks with no evidence of COPD exacerbation
- Weight of 40 kg-120 kg
- Willingness to use at least one form of acceptable birth control including abstinence, condom with spermicide, or hormonal contraceptives from time of signing ICF through study follow up visit
- Willing to monitor blood glucose if known history of diabetes mellitus requiring insulin or medical therapy
- Element of CFTR Dysfunction, as defined by Sweat Chloride $>$ 30 mEq/L

Exclusion Criteria

- Current Diagnosis of Asthma
- Known Diagnosis of Cystic Fibrosis
- Daytime use of Oxygen Therapy
- Documented history of drug abuse within the last year
- Subjects should not have a pulmonary exacerbation or changes in therapy for pulmonary disease within 28 days before receiving the first dose of study drug.
- Cirrhosis or elevated liver transaminases $>$ 3X ULN
- GFR $<$ 50 estimated by Cockroft-Gault
- Any illness or abnormal lab finding that, in the opinion of the investigator might confound the results of the study or pose an additional risk in administering study drug to the subject.
- Pregnant or Breastfeeding
- Subjects taking moderate or strong inhibitors or inducers of CYP3A4, including certain herbal medications and grapefruit juice. (Excluded medications and foods including the drugs and foods listed in the IRB HSP application.)
- Uncontrolled Diabetes
- Recent (e.g 1year) arterial thrombotic events (peripheral arterial disease, thrombotic stroke)

- Clinically significant arrhythmias requiring anti-arrhythmic agent(s) or conduction abnormalities that in the opinion of the investigator that affect patient safety such as the abnormalities listed below (patients with stable coronary artery disease are eligible)
 - ♦Angina symptoms
 - ♦History of MI
 - ♦Revascularization procedure in the last year prior to screening
 - ♦Clinically significant congestive heart failure (known LVEF $\leq 45\%$, cor pulmonale, diastolic heart failure, etc)

6.0 Statistical Analysis Plan

Safety analysis will be conducted by descriptive statistics. Pharmacodynamic analysis will be evaluated within group for the ivacaftor treatment group for changes between screening/day 1 and day 84. We will also compare findings between groups. The primary outcome measure is safety; the primary efficacy outcome measure is MCC (AUC₆₀) and change in FEV1 (% predicted). Secondary outcome measures including change in other measures of spirometry, PROs, exacerbation frequency, and 6MWD will also be analyzed. These data will be used to test the null hypothesis of no change using a paired t-test unless the distributions are notably skewed, in which case the non-parametric Wilcoxon signed-rank test will be implemented. Between group comparisons and composite time-dependent changes based on multiple measures (e.g. sweat chloride, MCC, FEV1, etc.) will be conducted as secondary analyses using the two-group t-test (or the non-parametric Wilcoxon rank-sum test if needed) and analysis of covariance models. The dose groups will be compared simultaneously using analysis of variance (or the nonparametric Kruskal-Wallis test if needed). Longitudinal analyses will consist primarily of mixed models repeated measures analyses. An appropriate structure for the covariance matrix will be selected for these models using the final data. When a model term is statistically significant, the Tukey-Kramer multiple comparisons test will be used to determine which specific pairs of means are significantly different. Interaction terms may be included in some models. All statistical tests will be two-sided and will use $\alpha=0.05$. Power analysis for measurements of MCC, CFTR function measured by sweat chloride, and FEV1 (% predicted) are provided below. The off drug effect will be measured by using data from the follow-up visit to assess the change from on drug to washout at the follow up visit.

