4.0 STUDY DESIGN

The study is a Phase 2 Study to establish the safety and efficacy of the CFTR potentiator ivacaftor in patients with chronic obstructive pulmonary disease (COPD), chronic bronchitis, and acquired CFTR dysfunction as detected by sweat chloride analysis. The design is a pilot, randomized (3:1, active:placebo), double-blind, placebo-controlled study to determine the safety and efficacy of ivacaftor (VX-770) in approximately 40 subjects with COPD.

Enrollment is planned at our single center, The University of Alabama at Birmingham. Patients will be randomized 3:1 to active drug (n=30) and placebo (10) to achieve the enrollment goal.

- A sufficient number of subjects will be screened to randomize up to 50 subjects to achieve 40 completed subjects to receive either ivacaftor 150 mg BID (n=30) or placebo (n=10) for 84 days.
- The schedule of assessments is shown in Table 1. The protocol design is shown in Figure 1.
- Ivacaftor and matching placebo will be orally administered as capsules according to the following guidelines:
 - Between study visit Day 1 and study visit Day 84, subjects will take 1 dose of study drug each day in the morning, beginning any time between 08:00 h (8:00 AM) and 12:00 h (12:00 PM). Whenever possible, subjects should take the study drug at the same time each day.

- On the study visit days when PK samples are collected (study visit Days 1, 28, 56, and 84), the study drug is to be taken by the subject while he/she is at the study site
- For visits after the Day 1 visit, subjects will be instructed to bring all remaining study drug materials to the site; study drug will be dispensed at each visit.
- Ivacaftor will be prepared and dispensed by an unblinded pharmacist.
- Subjects will be instructed to continue their standard COPD medication regimen.

Table 1. Schedule of Assessments ^a8 hr PK (pre, 1, 2, 4, 8, hr samples). ^b peak and trough PK only, ^crandom PK, ^donly if indicated.

Assessment	Screen (Day -28 to -1) Visit 1	Day 1	Day 28 (± 2)	Day 56 (± 2)	Day 84 (± 2)	Follow Up (Day 98 ± 2)
		Visit 2	Visit 3	Visit 4	Visit 5	Visit 6
Informed Consent	X					
Medical History & Concomitant Medications	X	X	X	X	X	X
Physical Examination	X	X	X	X	X	X
Safety Labs	X		X	X	X	X ^d
CFTR Genotyping	X					
Urine Pregnancy Test		X	X	X	X	X
Serum Pregnancy Test	X					
Blood Biomarker Collection		X	X	X	X	X
Spirometry	X	X	X	X	X	X
Sweat Chloride	X	X	X	X	X	X
MCC	X				X	
Patient report outcome questionnaires		X	X	X	X	X

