6.1 Power and Sample Size Calculations

The size of the study was chosen based on the ability to detect a meaningful within subject change in MCC and FEV1, while also providing a study population suitable to detect safety signals and determine clinical and physiologic outcome measures for future studies. The sample size was calculated for the target population (e.g. those with chronic bronchitis, which is associated with CFTR dysfunction¹³⁻¹⁶) based on prior experience with the CFTR endpoints and our knowledge of anticipated activity of ivacaftor in CF airway epithelia, which is substantiated based on the close relationship between CFTR activity *in vitro* and potential difference findings *in vivo* in CF subjects.¹⁷⁻²⁵ Choice of endpoints and sample size have also been informed by the pilot study.¹² Based on experience with ivacaftor using MCC imaging²⁶, and our preliminary data demonstrating sweat test abnormalities among COPD smokers (including repeated measures), our study also has sufficient power to detect changes in these parameters.^{27,28} Although we do not have sufficient data from the Pilot Study to perform an estimated sample size for changes in FEV1 with ivacaftor, we know from prior experience in COPD the variance of FEV1 in populations of this sort. Sample size calculations for key primary and secondary endpoints are shown in Table 2.

	Power based on response magnitude of	Within-
--	--------------------------------------	---------

Assay (unit)	Detectable difference		50% of the difference between COPD and normal		subject reproducibility (SD)
	80% Power	90% Power	Efficacy	Power	
MCC (AUC _{60 min})	3.9%	4.5%			7% ^{29,30}
Spirometry (FEV ₁) ^d	2.8% ^b	3.2%			5% ³¹
Sweat Chloride (mmol/L)	2.3	2.6	9.9 mmol/L	>99% ^a	4 mmol/L ^{18,32}

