Table 2. Power and sample size of the proposed study. All calculations are based on within subject changes observed with prior experience (as indicated by references in Table) or preliminary data, n=27 active treatment patients among all doses assignments and accounting for 10% drop-out rate, a two-sided paired t-test, and $\alpha=0.05$. ^aPower=80% between-groups at SD=12.8 mmol/L and 90% at SD=11.1 mmol/L. ^bPower=80% to detect 3.9% change in FEV₁% between groups; this corresponds to 5.1% relative improvement in FEV₁ assuming ~55% FEV₁% predicted upon enrollment, a typical mean value for COPD studies at our center with similar enrollment criteria. These two between-group calculations (a and b) assume a two-sided two-group t test. ^cThis is a conservative estimate based on extensive experience in NPD; within group SD is < 3 at our center. ^dBased on experience testing ivacaftor in CF patients, LCI exhibits even greater power than spirometry, so we have an excellent sample size to detect a meaningful effect.²⁸

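### The leading efficacy test of MCC and FEV1 is a before-after comparison within the ivacaftor arm, the placebo contrast is secondary, and its printed power fits 27 per arm, not the planned 3:1 allocation

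*Combined protocol and SAP*

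**What the plan says.** Section 4.0 sets the allocation: "Patients will be randomized 3:1 to active drug (n=30) and placebo (10) to achieve the enrollment goal".

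Section 6.0 ranks the outcomes ("The primary outcome measure is safety; the primary efficacy outcome measure is MCC", together with change in FEV1 % predicted) and gives the analysis: "Pharmacodynamic analysis will be evaluated within group for the ivacaftor treatment group for changes between screening/day 1 and day 84". It then adds that groups will also be compared. The test is a before-after one: "These data will be used to test the null hypothesis of no change using a paired t-test unless the distributions are notably skewed". Between-group comparisons, with sweat chloride, MCC and FEV1 as examples, "will be conducted as secondary analyses using the two-group t-test" or its rank-based counterpart, and analysis of covariance.

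Section 6.1 follows the same order: "The size of the study was chosen based on the ability to detect a meaningful within subject change in MCC and FEV1". Table 2 rests on "n=27 active treatment patients among all doses assignments and accounting for 10% drop-out rate, a two-sided paired t-test". Its footnotes a (sweat chloride) and b (FEV1) do give power against placebo: "These two between-group calculations (a and b) assume a two-sided two-group t test". Neither states a placebo sample size, and MCC has no between-group figure.

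The Statistical plan paragraph of the synopsis sets the ivacaftor change against placebo in unclear wording and ranks no test.

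**The concern.** The trial is randomised and placebo-controlled, and its stated purpose includes efficacy. Only the ivacaftor-minus-placebo difference uses the randomisation. A paired test in one arm asks whether patients changed over 84 days, for whatever reason: regression to the mean, learning, season, closer care or disease progression. Its 5% error rate does not apply to the question of drug versus placebo. A rise shared with placebo is liable to be read as benefit, and a shared decline can hide a real one.

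The footnotes add a second problem. A reader who turns to them for reassurance about the placebo contrast finds 80% and 90% power. If those figures assume a placebo arm three times the planned size, they overstate what about 9 placebo completers can show.

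**Working it through.** **Inputs.** Two-sided alpha 0.05 (Section 6.0). Allocation 30 and 10 (Section 4.0). Table 2: 27 active after 10% dropout from 30; SD 7 (MCC), 5 (FEV1) and 4 mmol/L (sweat chloride). Footnote b: 3.9 FEV1 points at 80% power, no SD given. Footnote a: 80% at SD 12.8 and 90% at SD 11.1, for the 9.9 mmol/L effect in Table 2. Assumption: the same 10% dropout on placebo, 10 × 0.9 = 9.

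**Formulas.** Power is the probability that a noncentral t exceeds its critical value.
- Paired: λ = δ / (σ/√n), n − 1 df.
- Two-group: λ = δ / (σ√(1/n₁ + 1/n₂)), n₁ + n₂ − 2 df.

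**1. The plan's paired figures.** At n=27 the differences detectable with 80% / 90% power are 3.92 / 4.54 for MCC (printed 3.9 / 4.5), 2.80 / 3.24 for FEV1 (2.8 / 3.2) and 2.24 / 2.59 for sweat chloride (2.3 / 2.6). They reproduce closely, so Table 2 uses its SDs directly as SDs of change.

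**2. The plan's between-group figures.** For FEV1 at 27 v 27, SE = 5√(2/27) = 1.361 and λ = 3.9/1.361 = 2.87, giving 80.3%. At 27 v 9, SE = 5√(1/27 + 1/9) = 1.925 and λ = 3.9/1.925 = 2.03. The critical value on 34 df is also 2.03, so power is about one half.

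| Arms | FEV1 3.9, SD 5 | Chloride 9.9, SD 12.8 | Chloride 9.9, SD 11.1 |
|---|---|---|---|
| Printed | 80% | 80% | 90% |
| 27 v 27 | 80.3% | 79.6% | 89.5% |
| 27 v 9 | 50.4% | 49.7% | 61.5% |
| 30 v 10 | 54.9% | 54.2% | 66.3% |
| 35 v 15 (Section 9.1 supply numbers, no dropout) | 69.7% | 69.0% | 80.8% |

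All three printed figures match 27 per arm, and none is reached at 35 v 15. For FEV1, 80% at 27 v 9 would need an SD of 3.5. Footnote a states its own SDs, so its mismatch cannot come from an assumed SD.

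**3. Shared change, no drug effect.** The documents give no placebo change, so the shifts are assumptions. Rejection rate of the paired test at n=27:

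| Shared shift | Table 2 SD as SD of change | Table 2 SD as per-measurement SD (× √2) |
|---|---|---|
| FEV1 0.5 point | 8% | 6% |
| FEV1 1 point | 17% | 11% |
| FEV1 2 points | 52% | 29% |
| MCC 1 point | 11% | 8% |
| MCC 2 points | 30% | 17% |

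The shift cancels in the two-group test, which stays at 5%.

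**4. Shared decline, true benefit equal to the Table 2 difference.** The paired test sees the net change. FEV1: 2.8 − 1 = 1.8 gives 44% and 2.8 − 2 = 0.8 gives 13%. MCC: 3.9 − 2 = 1.9 gives 27%. Without the decline, power is 80% for both.

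**5. What the placebo contrast can deliver at 27 v 9.** The 80%-power detectable difference is 7.8 points for MCC and 5.6 for FEV1. The 95% CI half-width is t × SE: 2.03 × 2.694 = 5.5 for MCC and 2.03 × 1.925 = 3.9 for FEV1.

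**The case against.** The strongest reply is that this is a pilot. The synopsis makes safety and PK primary and lists MCC and FEV1 under secondary objectives and endpoints. Section 6.1 is open about sizing on within-subject change. The two-group tests and ANCOVA will be run anyway, and no sentence says that a significant paired test establishes efficacy. This stands, and it limits the consequence to the efficacy conclusion. It does not make the before-after test answer the placebo question.

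The text can also be read more loosely. The sentence with the paired test follows the one on secondary outcomes, so Section 6.0 alone does not tie it to MCC and FEV1. Section 6.1 and Table 2 close that gap, because they size the trial on the paired test for exactly those two measures.

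On footnote a, the point about consequence is fair. At Table 2's own SD of 4, power for 9.9 mmol/L at 27 v 9 is above 99%, and still 99% at 4√2. The footnote misstates how large an SD the trial can tolerate; sweat chloride is not itself underpowered. The SD giving 80% at 27 v 9 is 8.9, not 12.8.

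The shared shifts are hypothetical, and small ones do little harm (8% for half an FEV1 point). The size of the error depends on them; the mismatch between test and question does not.

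Finally, Section 6.0 also plans mixed models for repeated measures, and FEV1 is measured at every visit. A mixed model that reports the Day 84 treatment difference would serve as well as ANCOVA for FEV1. MCC has only a screening and a Day 84 scan.

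**Conclusion.** The concern holds in both parts and should be fixed. The plan leads its efficacy analysis with a single-arm comparison and ranks the randomised contrast as secondary. The between-group power in footnotes a and b is wrong for this trial: about 50%, 50% and 61% at 27 v 9, or 55%, 54% and 66% at 30 v 10, against the printed 80%, 80% and 90%.

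The 27 v 9 figures assume equal 10% dropout, and the FEV1 figure takes Table 2's SD of 5 as the SD of change, as the table's paired calculations do. The sweat chloride figures use only SDs that footnote a prints. The inflated rejection rates rest on assumed shifts, but that the paired test cannot separate drug effect from shared change rests on no assumption. Safety and PK conclusions are not affected.

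**What to change.** In Section 6.0 and the synopsis:
- Make the ivacaftor-minus-placebo difference at Day 84, adjusted for baseline by ANCOVA and reported with its 95% CI, the leading efficacy analysis for MCC (AUC60) and FEV1 % predicted. For FEV1, the planned mixed model is acceptable if it is named in advance.
- Label the within-arm paired tests as supportive.
- Name one baseline per outcome in place of the combined screening and Day 1 reference: the Day 1 value, stated to be pre-dose, where one is collected, and the screening scan for MCC.
- Say that efficacy will be read as an estimate with its CI.

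In Table 2:
- Recompute footnotes a and b for 3:1, state both arm sizes and the SD used, and add MCC.
- Correct the relative change in footnote b: 3.9/55 = 7.1%. The printed 5.1% belongs to the paired difference, 2.8/55.

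The cost is wording and a recalculation, with no new patients, visits or data. The drawback is low power in the leading test. For the Table 2 differences (MCC 3.9, FEV1 2.8), the unadjusted two-group t-test has about 29% power at 27 v 9 and 32% at 30 v 10, or about 17% at 27 v 9 if the SDs are per-measurement. Baseline adjustment multiplies the variance of the change score by (1 + ρ)/2. At 27 v 9 (33 df) this gives about 30% power at an assumed baseline-to-Day-84 correlation of 0.9 and 37% at 0.5. The plan should state this low power openly; it is the reason to report an estimate with its interval.

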CFTR Genotyping: CFTR will be sequenced by commercially available procedures as performed by the John Hopkins University Genetics Laboratory. Analysis will be stratified by the presence and absence of CFTR mutations. Since we have a large pool of previously tested COPD patients, we will target our enrollment to those without known CFTR mutations.

Statistical plan: Safety analysis will be conducted by descriptive statistics. Pharmacodynamic analysis will be evaluated within group for the ivacaftor treatment group for changes between screening/day 1 and day 84, in comparison to between group changes in the placebo treatment group. The primary outcome measure is safety; the co-primary efficacy outcome measures are MCC (AUC₆₀) and change in FEV1 (% predicted). Power analysis for measurements of MCC, CFTR function measured by sweat chloride, and FEV1 (% predicted) are provided in below. Secondary outcome measures including change in other measures of spirometry, PROs, exacerbation frequency, and 6MWD will also be analyzed. The off drug effect will be measured by using data from the follow-up visit to assess the change from on drug to washout at the follow up visit.

Role of Vertex IIS:

- Vertex Pharmaceuticals will provide ivacaftor and matching placebo to randomize up to approximately 50 subjects to achieve approximately 40 completers (35 active patients and 15 placebo treated patients for 84 days, assuming 5 dropouts in the ivacaftor group and 5 dropouts in the placebo group). This will provide sufficient compound for lost samples, if they occur.
- To facilitate PK studies planned at UAB, we also request pure ivacaftor powder and stable isotope labeled internal standard for assay development and validation. We request 2-5 mg of each.

1.0 Rationale:

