9.0 Study Drug Administration and Management

Ivacaftor should be administered every 12 hours. It is recommended that subjects take ivacaftor approximately 30 minutes after the start of a meal or snack. Whenever possible subjects should take ivacaftor at the same time each day. On day 1 subjects who meet all inclusion and exclusion criteria will be enrolled in the study. In this study, all subjects will receive 150 mg ivacaftor BID or placebo. The research pharmacist will provide logs of investigation product and maintain those in a study binder.

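### Sweat chloride is both an entry criterion and an outcome, and the plan does not say whether its baseline is the Screening or the Day 1 value

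*Combined protocol and SAP*

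**What the plan says.** Section 5.0 and the synopsis list as an inclusion criterion "Element of CFTR Dysfunction, as defined by Sweat Chloride" above 30 mEq/L. The criterion does not name the visit at which it is judged. In Table 1 (section 4.0) sweat chloride and spirometry are marked at all six visits, so each has a Screening value and a separate Day 1 value. MCC has a pre-treatment value only at Screening; the questionnaires and the walk test have one only on Day 1.

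Section 6.0 states: "Pharmacodynamic analysis will be evaluated within group for the ivacaftor treatment group for changes between screening/day 1 and day 84". It continues: "These data will be used to test the null hypothesis of no change using a paired t-test", with a signed-rank test if the data are skewed. Between-group comparisons, with sweat chloride among the measures named, "will be conducted as secondary analyses using the two-group t-test" and analysis of covariance. The synopsis uses the same pair of visits and sets the within-group change "in comparison to between group changes in the placebo treatment group".

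Neither place says whether the starting value is Screening, Day 1 or their mean. The first dose is given at the Day 1 visit, and Table 1 does not say that Day 1 sweat chloride and spirometry come before it.

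**The concern.** A measurement that had to exceed a cut-off is, on average, too high by part of its own error, and a repeat will be lower with no treatment at all. Here the fall has the same sign as the effect ivacaftor is meant to produce. A one-arm test of no change cannot tell the two apart.

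Sweat chloride serves the first secondary objective (CFTR activity) and is the response in the PK/PD analysis of section 20.0. At stake is whether a null or small within-arm change could be declared significant because of how patients were selected. Leaving the baseline open also allows the choice to be made after the data are seen.

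FEV1, a named efficacy outcome, is also selected on (35-70% predicted) and has the same two candidate baselines. Its two cut-offs pull in opposite directions. Their midpoint, (35+70)/2 = 52.5%, is close to the 55% or so that Table 2's footnote assumes at enrolment, so the net bias is probably small.

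**Working it through.** **Inputs from the documents.** Cut-off 30 (5.0). From Table 2 and its notes: n=27 active, within-subject SD 4 mmol/L, two-sided paired t-test at 0.05, detectable change 2.3 (80% power) and 2.6 (90%), planned effect 9.9 mmol/L.

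**Assumptions (not in the documents).** Screened-population mean μ = 25-40 mmol/L; true between-patient SD s_b = 8-12 mmol/L; normal distributions; eligibility judged on the screening value only; no drug effect. The central case, μ = 30, puts half of patients above the cut-off. Its only anchor is the statement in 1.0 that about half of COPD patients have reduced CFTR activity, and equating that with a value above 30 is itself an assumption.

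**1. Reproduce Table 2.** Power is the noncentral t with 26 df and noncentrality δ√27/SD. With SD 4 the detectable δ is 2.24 (80%) and 2.59 (90%), against the stated 2.3 and 2.6. The 4 therefore acts as the SD of a change. If it were the SD of one test, the SD of change would be 4√2 = 5.66 and the 80% figure 3.17, which does not match. So the per-test error SD is s_e = 4/√2 = 2.83, and s_e² = 8.

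**2. Expected fall with no drug effect, screening baseline.** Fall = (s_e²/s_T) × φ(a)/(1−Φ(a)), with s_T = √(s_b²+s_e²) and a = (30−μ)/s_T. At μ = 30, a = 0 and the ratio is 0.798.
- s_b = 8: s_T = √72 = 8.49; fall = 8/8.49 × 0.798 = 0.75 mmol/L.
- s_b = 12: s_T = √152 = 12.33; fall = 8/12.33 × 0.798 = 0.52 mmol/L.

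**3. Rejection rate of the nominal 5% test, n=27, μ = 30.**
- Screening baseline: noncentrality = fall × √27/4 = 0.98 and 0.67, giving 15.6% and 9.9%.
- Mean of Screening and Day 1: the fall halves to 0.38 and 0.26; SD of change = 2.83 × √1.5 = 3.46; noncentrality 0.56 and 0.39, giving 8.4% and 6.6%.
- Day 1: fall 0, rejection 5%.

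A simulation of 20,000 trials of 27 patients per setting agreed to within about one percentage point.

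**4. Range over the assumed mean (s_b 8-12, screening baseline).**

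| μ | Share above 30 | Fall (mmol/L) | Rejection |
|---|---|---|---|
| 25 | 28-34% | 0.70-1.14 | 14-30% |
| 30 | 50% | 0.52-0.75 | 10-16% |
| 35 | 66-72% | 0.36-0.44 | 7-9% |
| 40 | 79-88% | 0.21-0.24 | 6% |

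**5. Scale, central case.** Against the detectable difference: 0.52/2.3 = 23% to 0.75/2.3 = 33%. Against the planned effect: 0.52/9.9 = 5% to 0.75/9.9 = 8%.

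**6. Between arms.** Selection precedes randomization, so the expected fall is equal in both arms and cancels. In simulation the difference was about 0 and the test rejected about 5% of the time.

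**The case against.** A reader might infer that the plan fixes the screening value as baseline and so books regression to the mean as an ivacaftor effect. The text does not say that. Some outcomes have a pre-treatment value only at Screening and others only on Day 1, so the slash can fairly be read as whichever visit holds the baseline. That reading stands for MCC, the questionnaires and the walk test. It settles nothing for sweat chloride and spirometry, where both visits hold one.

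A reader might also infer that the trial has no protection. It does: 6.0 plans a two-group test and ANCOVA, the synopsis refers to placebo, and the bias cancels there. But 6.0 makes those analyses secondary, the sample size rests on within-subject change, and only 10 placebo patients are planned. The within-arm result is therefore likely to carry weight.

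The highest rejection rate, 30%, needs μ = 25 and s_b = 8, where only about 28% of screened patients would qualify. Section 1.0 describes a population prioritized for CFTR dysfunction, which points to a higher share and a smaller bias. Reading Table 2's 4 as a per-test SD would enlarge the bias, but that reading does not reproduce the 2.3, so the enlarged bias should not be set against it.

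Finally, Day 1 is free of selection only if eligibility is not rechecked on it. Section 9.0 says "On day 1 subjects who meet all inclusion and exclusion criteria will be enrolled in the study", and no visit is named for the sweat test. This stands, and the fix has to close it.

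**Conclusion.** The point holds as an undefined baseline that permits a bias towards benefit, not as a bias already built in. The bias is full if Screening is used, half if the two visits are averaged, and nil with an unselected, pre-dose Day 1 value. In the central case the spurious fall is about 0.5-0.75 mmol/L and the false-positive rate of the within-arm test is about 10-16% from a screening baseline. Over assumed means of 25-40 the range is about 0.2-1.1 mmol/L and 6-30%. All of this rests on an assumed mean and between-patient SD.

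The bias could not imitate the planned 9.9 mmol/L effect, but it could make a null or small change significant. It touches one secondary pharmacodynamic endpoint and the PK/PD analysis that uses it, and probably FEV1 to a small degree. It does not touch MCC, which is not selected on, or the placebo comparisons. The change is worth making because it is nearly free; the documents do not support calling the sweat chloride analysis invalid.

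**What to change.** - In 6.0 and the synopsis, state that the baseline for sweat chloride and spirometry is the pre-dose Day 1 value, that the screening value alone decides sweat chloride and FEV1 eligibility, and that MCC keeps its screening baseline.
- Add a Table 1 footnote that Day 1 sweat chloride and spirometry precede the first dose.
- Use the same Day 1 value as the covariate in the planned between-group ANCOVA, and report that result alongside any within-arm sweat chloride result.

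Cost: a few sentences and a footnote, with no new assessment. The one loss is that the screening measurement no longer adds precision to the baseline: with the average the SD of change would be 3.46 rather than 4 mmol/L.

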Clinical Study Protocol

A Randomized, Double-blind, Phase 2, Placebo Controlled Study to Determine the Safety and Efficacy of Ivacaftor (VX-770) for the Treatment of Chronic Obstructive Pulmonary Disease (The Topic Trial)

9/2/2016

Principal Investigators: [name], MSPH

[name]

PROTOCOL SYNOPSIS

Title: A Randomized, Double-blind, Phase 2, Placebo Controlled Study to Determine the Safety and Efficacy of Ivacaftor (VX-770) for the Treatment of Chronic Obstructive Pulmonary Disease (The Topic Trial)

Lead Investigators: [name] MSPH
[name]
[name]
[name]
[contact]
Email: [contact]

[name] MD
[name]
[name]
[name]
[contact]
Email: [contact]

Clinical Phase Phase 2

Study Synopsis

General Description: The study is a Phase 2 Study to establish the safety and efficacy of the CFTR potentiator ivacaftor in patients with chronic obstructive pulmonary disease (COPD), chronic bronchitis, and acquired CFTR dysfunction as detected by sweat chloride analysis. The design is a pilot, randomized (3:1, active:placebo), double-blind, placebo-controlled study to determine the safety and efficacy of ivacaftor (VX-770). Approximately 40 subjects with COPD will be randomized (Figure 1).

Primary Objective:

1. Evaluate the safety of ivacaftor treatment in patients with COPD and chronic bronchitis
2. Evaluate the pharmacokinetics of ivacaftor in patients with COPD and chronic bronchitis

Secondary Objectives:

1. Measure the pharmacodynamics of ivacaftor on CFTR activity (Sweat Chloride, MCC) in COPD patients with chronic bronchitis
2. Measure the effect of ivacaftor treatment on clinical outcomes (spirometry, patient symptoms, 6 minute walk test) in COPD patients with chronic bronchitis

Primary Endpoint:

1. Safety as determined by adverse events, clinical laboratory values (serum chemistry, hematology, coagulation studies), standard digital ECGs, vital signs, and physical examinations

2. Pharmacokinetic parameters of ivacaftor in COPD subjects (8 hr day 1 PK and PK peak and trough concentrations on days 28, and 84. A random PK will be collected on day 56)

Secondary Endpoints:

1. Change in respiratory and peripheral CFTR activity as detected by sweat chloride and MCC respectively
2. Indicators of respiratory function and COPD health (Change in FEV₁% as detected by spirometry, secondary spirometry values (FVC%, FEV₁/FVC), 6 minute walk test

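### MCC and FEV1 are ranked as secondary in one place and as (co-)primary efficacy outcomes in two others, each tested and powered alone at 0.05, with no rule for what counts as efficacy success

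*Combined protocol and SAP*

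**What the plan says.** The documents rank the same two outcomes in three ways, all in current text.

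- **Synopsis, endpoint list.** The primary endpoints are safety ("Safety as determined by adverse events, clinical laboratory values" and further items) and pharmacokinetics. MCC is in the first secondary endpoint: "Change in respiratory and peripheral CFTR activity as detected by sweat chloride and MCC respectively". FEV1 is in the second, which opens "Indicators of respiratory function and COPD health".
- **Synopsis, Statistical plan.** Safety is primary, and "the co-primary efficacy outcome measures are MCC" (AUC60) and change in FEV1 (% predicted).
- **Section 6.0.** "The primary outcome measure is safety; the primary efficacy outcome measure is MCC" (AUC60) together with change in FEV1: a singular noun covering two variables. The secondary tier is then described separately: "Secondary outcome measures including change in other measures of spirometry, PROs, exacerbation frequency, and 6MWD will also be analyzed".

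On testing, Section 6.0 says "These data will be used to test the null hypothesis of no change using a paired t-test unless the distributions are notably skewed", with a signed-rank test otherwise. Between-group comparisons are labelled secondary analyses. On error control it says "All statistical tests will be two-sided and will use" a level of 0.05. The only multiplicity procedure is Tukey-Kramer, which compares pairs of means within a model and does not act across endpoints.

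Section 6.1 bases the study size on within-subject change in both MCC and FEV1. Table 2 powers each one separately.

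**The concern.** MCC and FEV1 cannot be both secondary and (co-)primary. The label alone would be a drafting matter, but it comes with a second gap: no section says what result on the pair would count as evidence of efficacy. With two tests at the full 0.05, the missing rule decides which property of the design fails. An either-endpoint rule gives up error control. A both-endpoints rule keeps it, but gives up the power that Table 2 appears to promise. A reader of the results could not tell whether a finding on one endpoint had met the plan's standard or had been picked after the fact.

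**Working it through.** **Inputs.** From Table 2 and its notes (Section 6.1): n = 27 active patients, two-sided paired t-test, alpha 0.05; SD 7% for MCC and 5% for FEV1, taken as the SD of the change. The documents give no correlation between the endpoints, so 0, 0.3 and 0.5 are assumptions.

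**1. Reproduce Table 2.** Power is taken from the noncentral t with 26 degrees of freedom and noncentrality (difference / SD) × √27.

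| Endpoint | Table 2 (80% / 90%) | Recomputed | Power at the stated values |
|---|---|---|---|
| MCC | 3.9 / 4.5 | 3.92 / 4.54 | 79.6% / 89.5% |
| FEV1 | 2.8 / 3.2 | 2.80 / 3.24 | 80.0% / 89.3% |

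The table reproduces, so each endpoint was powered alone at the full 0.05.

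**2. Either endpoint suffices.** If the tests are independent and both nulls are true, the chance of at least one false positive is 1 − 0.95² = 0.0975. For correlated tests, the bivariate normal gives 9.5% at correlation 0.3 and 9.1% at 0.5. The bound at any correlation is 0.05 + 0.05 = 0.10. Simulated paired t-tests at n = 27 agree: 9.6%, 9.4% and 9.2% at correlations 0, 0.3 and 0.5.

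**3. Both endpoints required.** The false-positive rate is at most 5%; if the tests are independent and both nulls are true, it is 0.05² = 0.25%. Joint power at the Table 2 80% differences (3.9 and 2.8) is 0.796 × 0.800 = 0.64 if independent. At correlation 0.5 the bivariate normal gives 0.69, and simulated t-tests at n = 27 give 0.68.

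**4. Holm at an overall 0.05.** The smaller p-value is compared with 0.025; if it passes, the other is compared with 0.05. If only one endpoint truly responds, it must in practice pass at 0.025:

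- power at 3.9 (MCC) is 69.6%, and at 2.8 (FEV1) 70.1%;
- the 80% detectable differences become 4.37 and 3.12, that is 4.4 and 3.1.

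Simulating the full Holm procedure with one responding endpoint gives 70% for each, and 4.7% to 4.9% overall error when neither responds.

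**5. Fixed sequence at 0.05.** The first endpoint keeps its Table 2 power. The second can be claimed only when both are significant, so its power at the stated differences is the joint figure from step 3, 64% to 69%.

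**The case against.** **The 10% is not a property of the plan as written.** A reader might infer that the trial runs a 10% efficacy error rate. The documents do not support that. The figure needs an either-endpoint rule, which is nowhere stated, and *co-primary* can mean that both must succeed, which caps the error at 5%. This objection stands. It does not clear the plan, because Section 6.0 drops the term, neither place defines it, and the both-endpoints reading has its own shortfall in power.

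**Nor is 10% a ceiling on false claims of drug effect.** It applies to a null of no change within the ivacaftor group. A shift unrelated to drug would push the paired test above its nominal level: with an assumed 1-point change in FEV1, SD 5 and n = 27, about 17% of tests would reject. Counting the between-group tests as further routes to success would give about 16% to 17% in simulation (27 active, 9 placebo, assumed correlation 0 to 0.5), but Section 6.0 labels those tests secondary. Whether a within-group test can show a drug effect is a separate issue. Its bearing here is that any success rule must name the contrast it governs.

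**The hierarchy conflict can be softened.** Safety is primary in all three places, and *primary efficacy outcome* could mean the lead measures beneath it. This is only partly persuasive, since Section 6.0 places other outcomes in the secondary tier. The absence of PK from the Section 6.0 ranking carries little weight: Section 20.0 gives PK its own analysis, which is parameter estimation and does not compete for alpha.

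**It is a pilot.** It plans about 40 completers and is meant to inform later trials. That limits the consequence. Against this, the title and design statement name efficacy alongside safety, and the study size was set on these two endpoints.

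**Conclusion.** The point holds. The endpoint labels contradict each other and no success rule is given. The size depends on the rule: 9.75% false positives if either endpoint suffices and the tests are independent (9.1% at an assumed correlation of 0.5, at most 10%), or joint power of about 64% to 69% against the 80% shown per endpoint if both are required. These figures assume one paired test per endpoint, the Table 2 SDs and n = 27; the error rates also assume no within-group change without drug. The documents give no ground for ranking MCC above FEV1, so they do not by themselves dictate a testing order. Safety conclusions are untouched. What changes is how an efficacy finding may be worded, and the point should be corrected on that footing.

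**What to change.** Use one hierarchy in the synopsis endpoint list, the synopsis statistical plan and Section 6.0: safety and PK primary, with MCC (AUC60) and FEV1 (% predicted) as the two lead efficacy outcomes. Before unblinding, pre-specify one success rule and the contrast to which it applies (within-group or between-group).

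- **Holm across the two at an overall 0.05** needs no ranking. Cost to state for the paired contrast: if only one endpoint responds, its power at the Table 2 80% difference is about 70%, and the 80% detectable differences rise to 4.4 (MCC) and 3.1 (FEV1).
- **A fixed sequence at 0.05** is acceptable if the sponsor chooses and states the order. Cost to state: the first endpoint keeps its Table 2 power, but the second has about 64% to 69% power for a formal claim.

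The power figures above are for the paired contrast at n = 27; if the between-group contrast is chosen, they must be recalculated for the 3:1 allocation. Otherwise the change is one of wording in the synopsis and Section 6.0, plus a note under Table 2 on power under the chosen rule. No extra patients are needed if the stated loss of power is accepted.
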